9. PRE-STUDY AND CONCOMITANT INTERVENTION/MEDICATION

Concomitant medications will not be documented during the study.

10. DEVIATIONS FROM THE PROTOCOL

Investigator will notify study sponsor upon identification of a protocol deviation. Major protocol deviations must be reported to the sponsor within 24 hours after discovery of the protocol deviation. The Investigator will report deviations per IRB/IEC requirements. All deviations will be tracked and corrective actions implemented as appropriate.

11. STUDY TERMINATION

Since all of the products associated with the study are marketed products, there are no anticipated circumstances in which the study would be prematurely terminated.

The Sponsor will determine if and when the study will be stopped. JJVC reserves the right to terminate the study at any time for any reason. Additionally, the IEC/IRB may reserve the right to terminate the study if an unreasonable risk is determined.

JJVC (and the IEC/IRB and DMC, if applicable) will evaluate all adverse events.

12. PROCEDURE FOR HANDLING PRODUCT QUALITY COMPLAINTS

Given the nature of the study, and since the subjects will be using normally marketed product, the monitoring of Product Quality Complaints (PQCs) is out of the scope of this study.

If the subject reports 'poor' overall comfort during a follow-up questionnaire, the subject will automatically be advised as part of the online questionnaire to consult their ECP.

13. ADVERSE EVENTS

This study is only concerned with ocular adverse events or adverse events related to the study lenses (test & control).

Investigators will not automatically report any adverse event. Instead, these will be captured by a question in the follow-up questionnaire regarding 'a problem with their eyes while wearing lenses that required them to visit an eyecare practitioner or hospital'. If subjects answer 'Yes' to this question the ECP investigator will be asked to complete a paper adverse

event form, detailing the problem. In the event of the subject having been seen by another clinic (e.g. emergency room) copies of the medical records will be requested.

The records of any adverse event will be reviewed by a Data Monitoring Committee (DMC) who will adjudicate the diagnosis, severity and causality of any adverse events.

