2.2. Endpoints

All of the primary and secondary endpoints will be assessed using the follow-up questionnaire administered at 2-weeks, 4-months and 12-months after the enrollment visit (Visit 1).

Primary endpoints

Vision Satisfaction in Bright Lighting

Subjects will be asked to evaluate their vision satisfaction in bright lighting by rating their level of agreement with the statement “I was satisfied with the quality of my vision in bright lighting with these contact lenses” using a 5-point agreement Likert scale (1: Strongly Disagree, 2: Disagree, 3: Neither Agree nor Disagree, 4: Agree and 5: Strongly Agree).

Secondary endpoints

Overall quality of vision

This will be assessed subjectively using the item “I am satisfied with the overall quality of my vision with these contact lenses”. The item uses a 5-point agreement scale (1: Strongly Disagree to 5: Strongly Agree)

Pulfrich Effect

This will be assessed subjectively using the item “While wearing these lenses, my depth perception of moving objects has NOT been impacted”. Subjects who disagree or strongly disagree with the statement will be considered to have experienced the Pulfrich effect.

Overall comfort

This will be assessed using the item “How would you rate the overall comfort of these contact lenses?”. The item uses the 5-point satisfaction scale, 1: Excellent, 2: Very Good, 3: Good, 4: Fair and 5: Poor.

Reported serious and significant ocular adverse events:

Incidence rate serious and significant ocular adverse events during the study period will be calculated (in 100 patient-year) using all available data from the entire study.

Other endpoint(s):

1. Overall satisfaction
2. Cosmetic appearance assessment
3. Lens storage compliance
4. Reasons for discontinuations
5. All reported ocular and non-ocular adverse events
6. Other subjective assessments (indoor performance, overall opinion, average wear time, etc.)

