13.1. Definitions and Classifications

Adverse Event (AE) – An AE is “any untoward medical occurrence, unintended disease or injury, or untoward clinical signs (including abnormal laboratory findings) in subjects, users or other persons, whether or not related to the investigational medical device.

NOTES:

Note 1 to entry: This definition includes events related to the investigational medical device or the comparator.

Note 2 to entry: This definition includes events related to the procedures involved.

Note 3 to entry: For users or other persons, this definition is restricted to events related to investigational medical devices.”¹

In this study, monitored AEs will be confined to ocular AEs or non-ocular AEs related to the study lenses (e.g. injury sustained through poor vision).

Serious Adverse Event (SAE) – An SAE is any untoward medical occurrence that:

- Is potentially sight-threatening
- Requires in-patient hospitalization or prolongation of existing hospitalization
- Results in persistent or significant disability/incapacity (e.g., a sight threatening event, a significant persistent or permanent change, impairment, damage, or disruption to the subject’s body)
- Requires intervention to prevent permanent damage (the use of the test article resulting in a condition which requires medical or surgical intervention to preclude permanent impairment of the body structure or a body function). Important medical events that may not result in death, be life-threatening, or require hospitalization may be considered an SAE when, based upon appropriate medical judgment, they may jeopardize the patient or subject and may require medical or surgical intervention to prevent one of the outcomes listed in the above definition

Diagnoses and conditions that are considered Ocular Serious Adverse Events include, but not limited to:

- Microbial Keratitis (MK)
- Iritis (including cells in the anterior chamber)
- Permanent decrease in best spectacle corrected visual acuity equivalent to 2 acuity lines or greater
- Central Corneal Opacity
- Central Corneal Neovascularization
- Uveitis
- Endophthalmitis
- Hypopyon

- Hyphema
- Penetration of Bowman's Membrane
- Persistent Epithelial Defect
- Limbal cell Damage

Significant Adverse Events – Those events that are usually symptomatic and warrant discontinuation (temporary or permanent) of the test article (excluding Serious Adverse Events).

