14.7. Other Exploratory Analyses

Subgroup analysis of the primary and secondary endpoints will be conducted by country, age group and lens material. Other subgroup analysis may be considered by factors showing interaction effects with the treatment. The control group will be categorized by lens materials and/or wear modality for further comparisons with the Test lens.

Further analysis using a generalized linear mixed model using Poisson or negative binomial distribution will be considered to test for statistical difference in incidence rates between Test and Control groups. Non-ocular lens related AEs will be evaluated.

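### Lens-related non-ocular adverse events are in scope, but the plan describes no systematic route for capturing them

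*Combined protocol and SAP*

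**What the plan says.** On scope, Section 13 opens: "This study is only concerned with ocular adverse events or adverse events related to the study lenses (test & control"). Section 13.1 is more explicit: "monitored AEs will be confined to ocular AEs or non-ocular AEs related to the study lenses (e.g. injury sustained through poor vision"). Section 2.2 includes among the 'other' endpoints "All reported ocular and non-ocular adverse events", and Section 14.7 ends with "Non-ocular lens related AEs will be evaluated".

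On capture, Section 13 states: "Investigators will not automatically report any adverse event". The next sentence gives the alternative route: "Instead, these will be captured by a question in the follow-up questionnaire regarding". The subject matter of that question is then set out as "a problem with their eyes while wearing lenses that required them to visit an eyecare practitioner or hospital". A positive reply starts the process: "to this question the ECP investigator will be asked to complete a paper adverse" (the sentence goes on to name the form). Where another clinic saw the subject, that clinic's records are requested, and the Data Monitoring Committee (DMC) adjudicates from the records.

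The synopsis (Study Design) and Section 13.3 repeat the same eye-problem trigger for obtaining medical records and for follow-up with the treating facility.

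**The concern.** The scope covers two kinds of event: ocular events, and non-ocular events related to the lenses. The question that starts the adverse event process addresses only the first. A subject who falls or has a road accident that they put down to how they saw through the lenses, and whose eyes are otherwise well, could truthfully answer 'No'. No form, record request or adjudication would then follow. This differs from dropout or non-response: the questionnaire is complete and the event is still missing, so the sensitivity analyses for missing data in Section 14.9 would not detect it.

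The gap matters more for this product than for an ordinary lens. Section 1 describes a lens that darkens in light, and Section 2.2 asks about depth perception of moving objects because of a possible Pulfrich effect. An injury is one plausible consequence of such an effect. Nothing in the plan says that an unfavourable answer to the depth-perception item starts any adverse event follow-up.

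**Working it through.** The plan gives no figure to reproduce on this point. The check is whether each declared kind of event has a route from occurrence to analysis.

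**Step 1: what is declared.** Lens-related non-ocular events are in scope or planned for analysis in four places:
- Section 13: general scope.
- Section 13.1: monitored events, with an injury as the example.
- Section 2.2: fifth 'other' endpoint.
- Section 14.7: exploratory evaluation.

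**Step 2: what starts the process.** The trigger is described in three places (synopsis, Section 13, Section 13.3). Each time it has the same three conditions: the problem is with the eyes, it arose while wearing lenses, and it required a practitioner or hospital visit. A non-ocular event can meet the second and third conditions and still fail the first.

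**Step 3: whether the procedures add another trigger.** They do not.
- The schedule in Section 7.1 shows the practitioner's adverse event form only as needed at each questionnaire.
- Steps 2.4, 3.4 and 4.4 of Section 7.2 provide for follow-up of events reported at that questionnaire.
- There is no scheduled visit after registration (Section 7.3), so no clinic contact exists at which an open question would be asked.

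**Step 4: what reaches analysis.**

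| Kind of event | In scope | Described trigger | Reaches form and DMC |
|---|---|---|---|
| Ocular, visit required | Yes | Yes | Yes |
| Non-ocular, lens-related | Yes | None | Only incidentally |

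**Step 5: what a count would mean.** Let p be the true risk of a non-ocular lens-related event per subject, s the fraction of such events that become recorded, and n the number of subjects in an arm. The expected number of subjects with a recorded event is n × p × s. The plan gives no basis for s, so the count does not determine p.

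For a zero count with complete capture (s = 1), the exact one-sided 95% upper bound on p is 1 − 0.05^(1/n):
- n = 300: 1 − 0.05^(1/300) = 0.99%
- n = 240: 1 − 0.05^(1/240) = 1.24%

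With incomplete capture these figures bound p × s, so the bounds on p become 0.99%/s and 1.24%/s. Both widen without limit as s falls towards zero. The formula shows why a low count is hard to interpret. It does not measure the shortfall, because s is unknown.

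**Step 6: what is not touched.** The secondary safety endpoint and the incidence rate in Section 14.6 are confined to serious and significant ocular events, which the trigger addresses. The primary endpoint is a questionnaire rating and does not depend on adverse event capture.

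**The case against.** The strongest reply is that the questionnaires are in Appendix A and the copy available for review does not show them. A further item or free-text field may exist there, and its absence from this copy is not evidence of its absence from the plan. That stands, and it limits the point to what the text describes. It does not remove the point, because Section 13 itself names a question on eye problems as the capture route and mentions no other.

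There are also incidental routes:
- A subject may read an injury caused by poor vision as an eye problem, and the question does mention hospital visits.
- Section 8.2 lists adverse events and safety judgement among the withdrawal reasons. The Final Form records the reason, and Section 14.8 has dropout reasons monitored.
- Section 15.2 expects the subject record to hold all adverse events.
- Section 18.3 sends serious, unanticipated, article-associated events to the ethics committee.
- Not reporting automatically is not the same as being forbidden to report.

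All of this is fair. None of it is planned, systematic collection of non-ocular events.

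A reader might therefore infer too much in three ways. The first is that such events cannot be recorded at all; the routes above contradict that. The second is that the question has a sensitivity near zero for them, so that a zero count supports no bound whatever; no sensitivity is documented, and the second half would follow only if it were exactly zero. The third is that the report will present a low count as evidence of safety; no section plans such a claim.

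Finally, the endpoint is worded as reported events, is missing from the synopsis list of 'other' endpoints and carries no hypothesis. The Pulfrich effect itself is asked about at all three assessments. This limits the importance of the gap. It does not reconcile the capture route with Section 13.1, which says the events are monitored, or with Section 14.7, which says they will be evaluated.

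**Conclusion.** The point holds as an internal inconsistency: the described capture route is narrower than the declared scope. Lens-related non-ocular adverse events have no defined systematic capture route, so they are liable to be under-collected, and a low or zero count could not be read as absence of such harm.

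The extent of under-collection is unknown and cannot be derived from the documents. The consequences are confined to one 'other' endpoint and one exploratory evaluation.

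The conclusion assumes that Section 13 describes the capture route completely. If Appendix A contains an item on non-ocular events, what remains is a missing cross-reference and a missing link to the adverse event process. The change is worth making because it is cheap and concerns safety data; the study's main conclusions do not depend on it.

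**What to change.** Add one item to the 2-week, 4-month and 12-month questionnaires. It should ask whether the subject has had any accident, fall, injury or other health problem that they think may be related to the lenses or to their vision with them. A 'Yes' should start the existing adverse event form, record request and DMC adjudication, and Sections 13 and 13.3 and the synopsis should say so. The online system is already meant to act on an answer, since Section 12 has it issue advice after a poor comfort rating. If Appendix A already holds such an item, cite it in Section 13 and link it to that process.

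The cost is a protocol and form amendment, one more online question at each assessment, and some unrelated reports to adjudicate out. If enrolment has already begun (the current version is dated November 2020; enrolment status is not given), capture will be uneven between earlier and later subjects, and the report should say so.

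If the sponsor prefers not to add the item, remove non-ocular events from Sections 2.2, 13.1 and 14.7. The opening scope sentence of Section 13 must be narrowed as well, or the contradiction remains there. The report should then state that non-ocular lens-related harm was not systematically assessed. This route costs only text, at the price of giving up a safety question that the plan itself raises.

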5.2. Masking

This is an open label registry study. The identity of the lenses is known to all. Given this, there are no procedures for maintaining and breaking the masking.

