13.2. Assessing Adverse Events

In conjunction with the medical monitor, the Investigator will evaluate adverse events to ensure the events are categorized correctly. Elements of categorization will include:

- Seriousness/Classifications (see definition in Section 13.1)
- Causality or Relatedness – i.e. the relationship between the test article, study treatment or study procedures and the adverse event (not related; unlikely related; possibly related; related - see definition in Section 13.2.1)
- Adverse Event Severity – Adverse event severity is used to assess the degree of intensity of the adverse event (mild; moderate; severe for all events - see definition in Section 13.2.2)
- Outcome – not recovered or not resolved; recovering or resolving; recovered or resolved with sequelae; recovered or resolved; death related to adverse event; unknown
- Actions Taken – none; temporarily discontinued; permanently discontinued; other.

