13.2.1. Causality Assessment

Causality Assessment – A determination of the relationship between an adverse event and the test article. The test article relationship for each adverse event should be determined by the investigator using these explanations:

- Not Related- An adverse event that is not related to the use of the test article, study treatment or study procedures
- Unlikely Related – An adverse event for which an alternative explanation is more likely, e.g. concomitant treatment, concomitant disease(s), or the relationship of time suggests that a causal relationship is not likely
- Possibly Related – An adverse event that might be due to the use of the test article, or to the study treatment or study procedures. An alternative explanation, e.g. concomitant treatment, concomitant disease(s), is inconclusive. The relationship in time is reasonable. Therefore, the causal relationship cannot be excluded
- Related – An adverse event that is listed as a possible adverse effect (device) or adverse reaction (drug) and cannot be reasonably explained by an alternative explanation, e.g. concomitant treatment of concomitant disease(s). The relationship in time is very suggestive, e.g. it is confirmed by de-challenge and re-challenge.

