13.2.2. Severity Assessment

Severity Assessment – A qualitative assessment of the degree of intensity of an adverse event as determined by the Investigator or reported to him/her by the subject. The assessment of severity is made irrespective of test article, study treatment or study procedure relationship or seriousness of the event and should be evaluated according to the following scale:

- Mild – Event is noticeable to the subject, but is easily tolerated and does not interfere with the subject's daily activities

- Moderate – Event is bothersome, possible requiring additional therapy, and may interfere with the subject's daily activities
- Severe – Event is intolerable, necessitates additional therapy or alteration of therapy and interferes with the subject's daily activities.

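### Entry into the serious/significant ocular event endpoint rests on judgement, yet the protocol text provides no lens-masked committee review and does not give the committee the deciding class

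*Combined protocol and SAP*

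**What the plan says.** **The endpoint.** Section 2.1 makes reported serious or significant adverse events one of the areas in which the Test lens is compared with non-photochromic lenses, and Section 2.2 makes them a secondary endpoint. Section 2.3 formulates no hypothesis about them and has rates and proportions calculated by arm. Section 14.6 gives the incidence formula and confirms that no hypothesis is tested. Section 14.7, under exploratory analyses, says a Poisson or negative binomial mixed model will be considered "to test for statistical difference in incidence rates between Test and Control groups".

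**Masking.** Section 5.2 states "The identity of the lenses is known to all" and that "there are no procedures for maintaining and breaking the masking". It makes no exception for the committee.

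**Who assesses events.**
- Section 13: the DMC reviews the records of any adverse event and is the body "who will adjudicate the diagnosis, severity and causality of any adverse events".
- Section 13.2: "In conjunction with the medical monitor, the Investigator will evaluate adverse events to ensure the events are categorized correctly". The listed elements include seriousness/classification, causality and severity.
- Section 13.2.1: "The test article relationship for each adverse event should be determined by the investigator using these explanations".
- Section 13.2.2: severity is "as determined by the Investigator or reported to him/her by the subject".
- Section 11: "JJVC (and the IEC/IRB and DMC, if applicable) will evaluate all adverse events".

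**The concern.** The borderline between classes is a matter of judgement. Section 13.1 separates significant from non-significant infiltrative events, uses a grade 3 threshold for other corneal findings, and defines the significant class partly by whether the event warrants stopping lens wear, and for corneal events by how long wear is stopped. An assessor who knows that the wearer has the sponsor's new photochromic lens may, without intending it, draw these lines differently in the two arms. That would be differential misclassification of a secondary endpoint.

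An open-label study can still mask its adjudicators, because they work from records and need not see the wearer. The protocol sets up the committee but does not use it for this purpose. Nor does it say that the committee settles the class, or whose class enters the Section 14.6 tables.

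**Working it through.** **1. What decides whether an event is counted.** The numerator in Section 14.6 is the number of subjects with a serious or significant ocular event. It has no filter on causality and none on the mild/moderate/severe grade. Section 13.1 defines adverse events regardless of relation to the device, and its significant list includes corneal events unrelated to lens wear. Section 13.2.2 grades severity irrespective of relationship or seriousness. Diagnosis and class therefore decide entry; causality and grade do not.

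**2. Who settles those two items.**

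| Item | Section 13 (DMC) | Sections 13.2 to 13.2.2 (investigator) | Enters the ocular rate? |
|---|---|---|---|
| Diagnosis | Yes | Not listed as an element | Yes |
| Serious/significant/non-significant class | Not listed | Yes, with medical monitor | Yes |
| Causality | Yes | Yes | No |
| Severity grade | Yes | Yes | No |

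The item that defines the endpoint most directly, the class, is the one not listed for the committee. Section 13.1 ties class largely to listed diagnoses, so an adjudicated diagnosis will usually settle it. The lists are open-ended, however, and some entries turn on discontinuation, so this does not cover every case. Section 13 states the committee's role without condition, while Section 11 qualifies it.

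**3. Is any of this masked?** Section 5.2 says no. Sections 13 to 13.4 describe no removal of lens information from the adverse event form or from outside medical records.

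**4. How much one judgement could matter.** The documents give no event rate, so these inputs are assumptions.
- Exposure per arm: 240 to 300 patient-years, taking one year for each of 240 completers or 300 enrolled subjects (Section 14.2).
- Rate: 0.5 to 4 serious or significant events per 100 patient-years (assumed).
- Expected events per arm = rate × patient-years / 100. Lowest: 0.5 × 240 / 100 = 1.2. Highest: 4 × 300 / 100 = 12.

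With equal true counts *k* and equal exposure, moving one Test event out of the class gives a rate ratio of (*k* − 1)/*k*. Moving one Control event out gives *k*/(*k* − 1).

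| True events per arm | One Test event moved out | One Control event moved out |
|---|---|---|
| 3 | 2/3 = 0.67 | 3/2 = 1.50 |
| 6 | 5/6 = 0.83 | 6/5 = 1.20 |
| 12 | 11/12 = 0.92 | 12/11 = 1.09 |

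**5. Against sampling error.** For 11 versus 12 events with equal exposure, the standard error of the log ratio is about √(1/11 + 1/12) = 0.417. The approximate 95% interval is 0.92 × exp(±1.96 × 0.417), or about 0.40 to 2.08. One reclassified event lies well inside that. It moves the point estimate visibly but would not by itself create a persuasive difference between arms.

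**The case against.** The case for leaving the plan alone has several parts.

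- *Investigator assessment followed by committee adjudication is an ordinary two-step process.* This stands. The word adjudicate, and the synopsis reference to an adjudicated diagnosis, suggest that the committee is final. A reader might infer that Sections 13 and 13.2.1 flatly contradict each other; the natural reading does not support that. What remains is that class is not on the committee's list, the analysed assessment is not named, and Section 11 qualifies the committee's role.
- *Disagreement over causality or severity cannot bias the ocular rate.* This stands in full. A reader might infer that the split of those roles biases the comparison, but neither item enters the endpoint. Causality matters only for non-ocular lens-related events (Sections 13.1 and 14.7) and for device effects. Unclear responsibility is also not, by itself, bias that differs by arm.
- *There is no formal comparison to protect.* This stands in part. A reader might infer that Section 14.7 commits to a between-arm test; it only says one will be considered. But the objective is worded as a comparison, and rates printed by arm will be compared.
- *It is not shown that the committee sees the lens.* This is fair. It is inferred from the general statement in Section 5.2. No committee charter or adverse event form is in the text supplied, nor is the stand-alone SAP that Section 14.1 announces. The supportable statement is that the protocol text provides no masked review.
- *Redaction may hinder causality review.* This stands. Section 13.2.1 defines a related event partly by whether it is a listed possible effect of the device, so causality review may need lens identity. The fix must allow for it.

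**Conclusion.** The point holds as a cheap improvement, not as an error that endangers the study. Diagnosis and class decide which events count, both involve judgement, and the protocol text provides no lens-masked review for the body it sets up to adjudicate. It also leaves the class with the investigator and medical monitor, and does not say whose class is analysed.

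The size of the effect is not computable from the documents. Under the stated assumptions (3, 6 or 12 true events per arm, equal exposure), one Test event moved out of the class gives a ratio of 0.67, 0.83 or 0.92. The documents give no reason to expect a particular direction and no evidence that misclassification will occur.

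A reader might infer that the main result is at risk. It is not: the primary endpoint is the subject's own rating of vision in bright lighting, and adverse event classification plays no part in it.

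**What to change.** 1. Have the CRO remove lens brand and photochromic status, where feasible, from event forms and medical records before they reach the committee. Section 15.1 already routes investigators' paper forms through the CRO before data entry.
2. State in Section 13 that the committee adjudicates diagnosis and the serious/significant/non-significant class on the masked records, and reviews causality afterwards with lens identity available.
3. State in Section 14.6 that the tables use the committee's masked class, with the investigator's class listed alongside.
4. Reconcile Section 11, Section 13 and Sections 13.2 to 13.2.2 on who assesses events and whether the committee's role is conditional.

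**Cost.** A few sentences, redaction of a small number of records (about 1 to 12 serious or significant events per arm under the assumed rates, plus other reported events), and a two-step committee review. These changes should be made before event data are reviewed by arm.

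**Limit.** Masking the committee cannot remove bias that enters earlier, through the subject's self-report that triggers capture or through lens-discontinuation decisions already made in routine care.
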